#### 8.1.3 Reporting period

Details of all AEs and SAEs (except those listed above) will be documented and reported from the date of commencement of protocol defined treatment until 28 days after the administration of the last treatment. SAEs that are judged to be at least possibly related to any of the trial IMPs must still be reported in an expedited manner irrespective of how long after IMP administration the reaction occurred.

# 8.2 Reporting Requirements – Observational Component

#### 8.2.1 Serious Adverse Advents

For patients recruited to the observational component, Investigators should only report AEs that meet the definition of a Serious Adverse Event (SAE) (see Appendix 3 for definition) and are at least possibly related to a trial specific procedure. Any AE related to the patient's current disease or treatment is explicitly excluded from the reporting process.

# 8.2.2 Reporting period

SAEs related to trial specific procedures will be documented and reported from the date of registration until 28 days after completion of the last protocol assessment.

# 8.3 Reporting Procedure

### 8.3.1 Site

#### 8.3.1.1 Adverse Events

AEs should be reported on an AE Form (and where applicable on an SAE Form). An AE Form should be completed at each visit and returned to the Trials Office.

AEs will be reviewed using the CTCAE, version 4.0 (see Appendix 4). Any AEs experienced by the patient but not included in the CTCAE should be graded by an Investigator and recorded on the AE Form using a scale of (1) mild, (2) moderate or (3) severe. For each sign/symptom, the highest grade observed since the last visit should be recorded.

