#### 8.1.2.1 Events that do not require reporting on a Serious Adverse Event Form

The following events should not be reported on an SAE Form:

- Hospitalisations for:
  - o Pre-planned elective procedures unless the condition worsens

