#### 8.3.1.2 Serious Adverse Events

For more detailed instructions on SAE reporting refer to the SAE Form Completion Guidelines contained in the ISF.

AEs defined as serious and which require reporting as an SAE (excluding events listed in Section 8.1 or 8.2 above) should be reported on an SAE Form. When completing the form, the Investigator will be asked to define the causality and the severity of the AE which should be documented using the CTCAE version 4.0.

On becoming aware that a patient has experienced an SAE, the Investigator (or delegate) must complete, date and sign an SAE Form. The form should be faxed together with a SAE Fax Cover Sheet to the Trials Office using one of the numbers listed below as soon as possible and no later than 24 hours after first becoming aware of the event:

To report an SAE, either e-mail or fax the SAE Form with an SAE Fax Cover Sheet to:

[name] or [name]

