# **12.2 Definition of Outcome Measures**

#### 12.2.1 Interventional Component

#### **12.2.1.1 Primary outcome measures**

MTD of ruxolitinib in combination with 5-azacitidine in patients with advanced phase MPNs as defined by the number of reported DLTs (as defined in section 2.2) occurring within the first cycle of treatment (first 28 days).

Safety of ruxolitinib in combination with 5-azacitidine will be assessed using the CTCAE v4.0 criteria.

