# Serious Adverse Event

Any untoward medical occurrence or effect that at any dose:

- Results in death
- Is life-threatening\*
- Requires hospitalisation\*\* or prolongation of existing inpatients' hospitalisation
- Results in persistent or significant disability or incapacity
- Is a congenital anomaly/birth defect
- Or is otherwise considered medically significant by the Investigator\*\*\*

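### The AE Form scale for events outside the CTCAE stops at severe, so a life-threatening or fatal unlisted event can carry one grade there and another on the SAE Form

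*Protocol*

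**What the plan says.** Section 8.3.1.1 grades adverse events by CTCAE v4.0 and adds a fallback for events the CTCAE does not contain: "Any AEs experienced by the patient but not included in the CTCAE should be graded by an Investigator". The fallback has three values only, since such an event is to be "recorded on the AE Form using a scale of (1) mild, (2) moderate or (3) severe". The same section directs one event to one or both forms: "AEs should be reported on an AE Form (and where applicable on an SAE Form").

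For the SAE Form, section 8.3.1.2 asks the investigator to "define the causality and the severity of the AE which should be documented using the CTCAE version 4.0". It makes no exception for unlisted events.

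Appendix 3 defines an SAE to include any event that "Results in death" or "Is life-threatening". For the interventional component, section 8.1.2.1 keeps only one kind of event off the SAE Form, hospitalisation for "Pre-planned elective procedures unless the condition worsens".

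On the analysis side, section 12.2.1.1 states: "Safety of ruxolitinib in combination with 5-azacitidine will be assessed using the CTCAE v4.0 criteria". Section 12.3 likewise reports DLTs and AEs descriptively by CTCAE v4.0.

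**The concern.** The fallback scale is shorter than the scale it stands in for. The protocol itself uses a grade above 3, because the DLT definition in section 2.2 covers grades 3 and 4. The AE Form scale for unlisted events has no such value, so three different degrees of severity merge into one number.

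Sections 8.3.1.1 and 8.3.1.2 also set different severity rules for the same serious unlisted event, and neither says which prevails. Safety is part of the primary objective (section 2.1), and section 1.2.3 describes prior experience of the combination in three patients with AML after MPN. Unlisted serious events are ones a dose-finding study of this combination should record consistently. If the AE tables are built from the AE Form, the most severe unlisted events would appear one or two grades too low.

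**Working it through.** No design figure is involved, so the check sets the rules side by side for an adverse event that the CTCAE does not include, in the interventional component.

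| True severity | AE Form (8.3.1.1) | SAE by definition (Appendix 3)? | SAE Form (8.3.1.2) |
|---|---|---|---|
| Severe, not life-threatening | 3 | Only if another seriousness criterion is met | CTCAE v4.0, if an SAE |
| Life-threatening | 3 (highest value) | Yes | CTCAE v4.0 |
| Fatal | 3 (highest value) | Yes | CTCAE v4.0 |

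1. **Is the AE Form capped?** Yes. The last two rows cannot be told apart from the first on that form.

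2. **Is the information lost to the trial?** No. Both rows are SAEs, and the single exclusion in section 8.1.2.1 does not cover them. An SAE Form graded by CTCAE v4.0 is always due.

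3. **Can the two forms disagree?** Yes, if each rule is followed literally. Taking life-threatening as grade 4 and death as grade 5, the AE Form is lower by 4 − 3 = 1 or 5 − 3 = 2 grades. The protocol cites the CTCAE without reproducing its grades (Appendix 4), so this mapping is the usual convention and not a protocol figure. The mismatch already holds on grade 4, which the protocol uses.

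4. **Does it reach the primary outcome?** For a life-threatening event, 3 and 4 both lie within the grades named in the DLT definition. The DLT count and the CRM input are the same either way.

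5. **What about a related fatal event?** Recorded as 3 on the AE Form, it falls within the literal DLT wording. Recorded above 4 on the SAE Form, it falls outside. The replacement rule in section 2.2 gives as its example only a death considered unrelated to treatment. This does not show that such a death would be miscounted. It shows that the DLT wording should be read alongside any change to the scale.

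6. **How many events?** The protocol gives no rate. As an assumption only, if 1% to 5% of the 34 interventional patients had an unlisted life-threatening or fatal event, the number would be 0.01 × 34 = 0.34 to 0.05 × 34 = 1.7 patients, so roughly none to two.

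**The case against.** The strongest reply is that nothing important depends on the AE Form value. SAE Forms are due within 24 hours (8.3.1.2), the trials office assesses seriousness and causality independently (8.3.2), fatal or life-threatening SUSARs go to the regulator and ethics committee within 7 days (8.3.3.1), and the TSC reviews all SAEs (8.3.5). Deaths also enter overall survival. All of this stands, and it is why the point is minor.

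Four stronger readings are tempting, and the protocol does not support them:

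- A reader might infer that such an event can be recorded in the trial only as grade 3. That is true of the AE Form alone.
- A reader might infer that the 1 to 3 values share a field with CTCAE grades and are tabulated together, so that counts of grade 4 and 5 events are certain to be too low. The form is not shown, and which form supplies the grade may be settled in the SAP. Understatement follows only if the AE Form is the source.
- A reader might infer that the two records cannot be reconciled. Each SAE has a unique reference number (8.3.1.2), and central monitoring checks data consistency and raises queries (10.3).
- A reader might infer that dose recommendations are distorted. Recording 3 in place of 4 does not change them.

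What remains is that the protocol fixes the shorter scale when the data are captured. A SAP can choose the source form, but it cannot recover from the AE Form a distinction that was never entered there. Section 9.1 puts CRFs in the electronic system and keeps SAE reporting on paper, so the fuller grade is held apart from the electronic AE data.

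**Conclusion.** The point holds as a small inconsistency in recording rules. Sections 8.3.1.1 and 8.3.1.2, followed as written, give a life-threatening or fatal unlisted event two different severity rules. The AE Form rule is capped and does not match the CTCAE v4.0 basis on which safety is to be reported. No sample size, DLT count for a life-threatening event or CRM recommendation changes, and the severity remains on the SAE Form. The number of events is probably very small; the range of none to about two patients rests on an assumed rate, not on the protocol. It is a low-priority change, worth making because it is nearly free.

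**What to change.** In section 8.3.1.1, give unlisted events the same five-point range as the CTCAE by adding 4 (life-threatening) and 5 (death) to the existing three values. Require the same grade on the AE Form and the SAE Form, and cross-refer to this in 8.3.1.2. When making the change, check that the grade wording of the DLT definition in section 2.2 is reconciled with how a related fatal event is counted; how it should count is for the trial team to state.

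The cost is one sentence, a cross-reference and two extra options on the AE Form. There is no consequence for the sample size or the analysis. Any unlisted serious events already recorded would need their AE Form grade checked against the SAE Form.

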#### 8.3.1.2 Serious Adverse Events

For more detailed instructions on SAE reporting refer to the SAE Form Completion Guidelines contained in the ISF.

AEs defined as serious and which require reporting as an SAE (excluding events listed in Section 8.1 or 8.2 above) should be reported on an SAE Form. When completing the form, the Investigator will be asked to define the causality and the severity of the AE which should be documented using the CTCAE version 4.0.

On becoming aware that a patient has experienced an SAE, the Investigator (or delegate) must complete, date and sign an SAE Form. The form should be faxed together with a SAE Fax Cover Sheet to the Trials Office using one of the numbers listed below as soon as possible and no later than 24 hours after first becoming aware of the event:

To report an SAE, either e-mail or fax the SAE Form with an SAE Fax Cover Sheet to:

[name] or [name]

#### Or [contact]

On receipt the Trials Office will allocate each SAE a unique reference number. This number will be transcribed onto the SAE Fax Cover Sheet which will then be faxed/e-mailed back to the site as proof of receipt. If confirmation of receipt is not received within 1 working day please contact the Trials Office. The SAE reference number should be quoted on all correspondence and follow-up reports regarding the SAE. The SAE Fax Cover Sheet completed by the Trials Office should be filed with the SAE Form in the ISF.

For SAE Forms completed by someone other than the Investigator the Investigator will be required to countersign the original SAE Form to confirm agreement with the causality and severity assessments. The form should then be returned to the Trials Office in the post and a copy kept in the ISF.

Investigators should also report SAEs to their own Trust in accordance with local practice.

#### 8.3.1.3 Provision of follow-up information

Patients should be followed up until resolution or stabilisation of the event. Follow-up information should be provided on a new SAE Form (refer to the SAE Form Completion Guidelines for further information).

# 8.3.2 Trials Office

On receipt of an SAE Form seriousness and causality will be determined independently by a Clinical Coordinator. An SAE judged by the Investigator or Clinical Coordinator to have a reasonable causal relationship with the trial medication will be regarded as a Serious Adverse Reaction (SAR). The Clinical Coordinator will also assess all SARs for expectedness. If the event meets the definition of a SAR that is unexpected (i.e. is not defined in the Summary of Product Characteristics) it will be classified as a Suspected Unexpected Serious Adverse Reaction (SUSAR).

### 8.3.3 Reporting to the Competent Authority and main Research Ethics Committee

#### 8.3.3.1 Suspected Unexpected Serious Adverse Reactions

The Trials Office will report a minimal data set of all individual events categorised as a fatal or life threatening SUSAR to the Medicines and Healthcare products Regulatory Agency (MHRA) and main Research Ethics Committee (REC) within 7 days. Detailed follow-up information will be provided within an additional 8 days.

All other events categorised as SUSARs will be reported within 15 days.

#### 8.3.3.2 Serious Adverse Reactions

The Trials Office will report details of all SARs (including SUSARs) to the MHRA and main REC annually from the date of the Clinical Trial Authorisation, in the form of a development safety update report (DSUR).

#### 8.3.3.3 Adverse Events

Details of all AEs will be reported to the MHRA on request.

#### 8.3.3.4 Other safety issues identified during the course of the trial

The MHRA and main REC will be notified immediately if a significant safety issue is identified during the course of the trial.

#### 8.3.4 Investigators

Details of all SUSARs and any other safety issue which arises during the course of the trial will be reported to Principal Investigators. A copy of any such correspondence should be filed in the ISF.

#### 8.3.5 Trial Steering Committee

The independent Trial Steering Committee (TSC) will review all SAEs.

#### 8.3.6 Manufacturer of Investigational Medicinal Product

All SAEs will be reported to the manufacturer of the Investigational Medicinal Product within 24 hours by fax.

#### 8.3.7 Investigators

Details of all Unexpected and Related SAEs and any other safety issue which arises during the course of the trial will be reported to Principal Investigators. A copy of any such correspondence should be filed in the ISF.

# 9. DATA HANDLING AND RECORD KEEPING

# 9.1 Electronic Data Collection

The Case Report Form (CRF) will comprise a set of forms capturing details of eligibility, baseline characteristics, treatment and outcome details. There will be a separate CRF for the Interventional Component and the Observational Component.

This trial will use an electronic data capture (EDC) system which will be used for completion of CRFs.

Access to the EDC system will be granted to individuals via the Trials Office. SAE reporting and Notification of Pregnancy will be paper-based.

The CRF must be completed by the Investigator or an authorised member of the site research team (as delegated on the Site Signature and Delegation Log) within specified timeframes (found in the eCRF completion guidelines). The exceptions to this are the SAE Form and Withdrawal Form which must be co-signed by the Investigator.

Entries on the paper CRF should be made in ballpoint pen, in blue or black ink, and must be legible. Any errors should be crossed out with a single stroke, the correction inserted and the change initialled and dated. If it is not obvious why a change has been made, an explanation should be written next to the change.

Data reported on each form should be consistent with the source data or the discrepancies should be explained. If information is not known, this must be clearly indicated on the form. All missing and ambiguous data will be queried. All sections are to be completed before returning.

In all cases it remains the responsibility of the Investigator to ensure that the CRF has been completed correctly and that the data are accurate.

The completed originals (of the paper forms) should be sent to the Trials Office and a copy filed in the Investigator Site File.

Trial forms may be amended by the Trials Office, as appropriate, throughout the duration of the trial. Whilst this will not constitute a protocol amendment, new versions of the form must be implemented by participating sites immediately on receipt.

# 9.2 Archiving

It is the responsibility of the Principal Investigator to ensure all essential trial documentation and source records (e.g. signed Informed Consent Forms, ISFs, Pharmacy Files, patients' hospital notes, copies of CRFs etc.) at their site are securely retained for at least 10 years after the end of the trial. Do not destroy any documents without prior approval from the CRCTU Document Storage Manager.

# **10. QUALITY MANAGEMENT**

# **10.1 Site Set-up and Initiation**

All sites will be required to sign a Clinical Study Site Agreement prior to participation. In addition all participating Investigators will be asked to sign the necessary agreements e.g. registration forms and supply a current CV to the Trials Office. All members of the site research team will also be required to sign the Site Signature and Delegation Log, which should be returned to the Trials Office. Prior to commencing recruitment all sites will undergo a process of initiation. Key members of the site research team will be required to attend either a meeting or a teleconference covering aspects of the trial design, protocol procedures, Adverse Event reporting, collection and reporting of data and record keeping. Sites will be provided with an ISF and a Pharmacy File containing essential documentation, instructions, and other documentation required for the conduct of the trial. The Trials Office must be informed immediately of any change in the site research team.

# **10.2 On-site Monitoring**

Monitoring will be carried out as required following a risk assessment and as documented in the CRCTU Quality Management Plan. Additional on-site monitoring visits may be triggered for example by poor CRF return, poor data quality, low SAE reporting rates, excessive number of patient withdrawals or deviations. If a monitoring visit is required the Trials Office will contact the site to arrange a date for the proposed visit and will provide the site with written confirmation. Investigators will allow the PHAZAR trial staff access to source documents as requested.

# **10.3 Central Monitoring**

Where a patient has given explicit consent sites are requested to send in copies of signed Informed Consent Forms for in-house review.

Trials staff will be in regular contact with the site research team to check on progress and address any queries that they may have. Trials staff will check incoming CRFs for compliance with the protocol, data consistency, missing data and timing. Sites will be sent Data Clarification Forms (DCFs) requesting missing data or clarification of inconsistencies or discrepancies.

Sites may be suspended from further recruitment in the event of serious and persistent noncompliance with the protocol and/or GCP, and/or poor recruitment. Any major problems identified during monitoring may be reported to the Trial Management Group and the relevant regulatory bodies. This includes reporting serious breaches of GCP and/or the trial protocol to the main REC and the MHRA.

# **10.4 Audit and Inspection**

The Investigator will permit trial-related monitoring, audits, ethical review, and regulatory inspection(s) at their site, providing direct access to source data/documents.

Sites are also requested to notify the Trials Office of any MHRA inspections.

# **10.5 Notification of Serious Breaches**

In accordance with Regulation 29A of the Medicines for Human Use (Clinical Trials) Regulations 2004 and its amendments the Sponsor of the trial is responsible for notifying the licensing authority in writing of any serious breach of:

- The conditions and principles of GCP in connection with that trial or;
- The protocol relating to that trial, within 7 days of becoming aware of that breach

For the purposes of this regulation, a "serious breach" is a breach which is likely to effect to a significant degree:

- The safety or physical or mental integrity of the subjects of the trial; or
- The scientific value of the trial

Sites are therefore requested to notify the Trials Office of a suspected trial-related serious breach of GCP and/or the trial protocol. Where the Trials Office is investigating whether or not a serious breach has occurred sites are also requested to cooperate with the Trials Office in providing sufficient information to report the breach to the MHRA where required and in undertaking any corrective and/or preventive action.

# **11. END OF TRIAL DEFINITION**

The end of trial will be 6 months after the last data capture. This will allow sufficient time for the completion of protocol procedures, data collection and data input. The Trials Office will notify the MHRA and main REC that the trial has ended and will provide them with a summary of the clinical trial report within 12 months of the end of trial.

# **12. STATISTICAL CONSIDERATIONS**

# 12.1 Trial Design

# **Observational Component**

Up to 30 patients will be recruited into an observational component. Data concerning their treatments and outcomes will be collected and they will also have the option of contributing samples for biobanking over a 6 month period. No direct comparison will be made between the two components in terms of outcome measures.

#### Interventional Component

The primary objective of the trial is to establish the MTD of ruxolitinib in combination with 5-azacitidine using a restricted 2-stage Bayesian CRM [15-17]. The target DLT probability for the trial combination therapy is 25%. The prior estimation of MTD is at dose level 3, however to exercise caution, dose level

0 is defined as the starting dose. Patients will be assigned to dose combinations in cohorts of up to 5 patients.

In the first stage, the first cohort will be enrolled at dose level 0. If none experiences a DLT, the next cohort will be recruited at the next higher level (i.e. dose level 1). This process continues until the first DLT is observed in a cohort. Once there is a DLT, the second stage which comprises of the model based CRM begins.

In the second stage, we will utilise an empiric dose-toxicity model,  $F(x,\beta)$  given as

 $F(x,\beta) = x^{\exp(\beta)}$  for 0 < x < 1,

where the model parameter  $\beta$  is estimated using Bayesian analysis and *x* comprises of the initial guesses of probability of DLT at each dose level.

The recommended dose for the next cohort will be made using the CRM taking into account all the previous data observed including the first stage. This would be the dose with estimated DLT probability closest to the target of 25%. Subsequent cohorts will be assigned a dose level in the same way using all previous data observed until the MTD is declared or the maximum sample size is reached.

The five dose levels scheduled for a combination of ruxolitinib and azacitidine, together with the prior probabilities of DLT, are presented in Table 2. The prior guess of MTD is at dose level 3, but to exercise caution as this combination regimen has not been well studied in this patient population, dose level 0 (75 mg/m^2 azacitidine and 10 mg ruxolitinib bd) is defined as the starting dose. If the starting combination dose is too toxic, the design allows for de-escalation to dose -1. If the combination therapy is found to be tolerable, we would then escalate to higher doses of ruxolitinib.

Dose Level	Azacitidine dose	Ruxolitinib dose (bd)	Prior Probability of DLT		
-1	75mg/m 	5 mg	0.05		
0 (starting dose)	75mg/m 	10 mg	0.10		
1	75mg/m 	15 mg	0.15		
2	75mg/m 	20 mg	0.20		
3	75mg/m 	25 mg	0.25		

Table 2: Dose levels with initial guesses of probability of DLT at each level

We will apply restrictions to avoid skipping dose levels in escalation, as well as to ensure no immediate escalation if observed toxicity at the current dose level is greater than the target toxicity level. A "look ahead" strategy will be implemented if the next recommended dose level by the CRM model is the same regardless of the outcome of the remaining patient(s) in the current cohort (DLT or no DLT). If that occurs, we could consider recruiting patients for the next cohort. By implementing this strategy, we enable the next cohort of patients to be recruited immediately before observing all the patients' outcomes in the current cohort (whenever such a scenario occurs). This has the advantage of reducing waiting time between cohorts.

We plan to accrue 34 patients. Once recruitment is completed, the MTD will be declared as the combination dose with associated DLT rate closest to the target of 25%.

